6.11 Concomitant Medication Assessments

All concomitant medications (including any blood or blood products) and/or concomitant procedures administered or performed during the study will be recorded in the source record and subsequently captured in the eCRF (including date, time, type of medication or product, and dose or amount).

6.11.1 Excluded Medications

As was stated in [Exclusion Criterion 12](#), the use of aspirin, NSAIDs, herbs, natural medications, or other drugs with platelet inhibitory properties are excluded one week prior to surgical procedure and for the duration of treatment with LR769.

6.12 Study Stopping Rules

The study will be stopped (ie, cease enrollment as well as treatment of already enrolled patients) in the following cases:

- A confirmed thrombotic event has been reported in any of the patients treated in the study
- An acute allergic or anaphylactic reaction, or signs and symptoms strongly indicative of such reaction, has occurred in association with the administration of LR769
- A patient develops a neutralizing antibody to LR769

If one of these events occurs, participating sites, competent authorities, as well as all involved ECs/IRBs, will be informed of the (temporary) stop of the study. Investigations into the case(s) will need to be done and the results will then be reported to the competent authorities and ECs/IRBs, together with a recommendation on whether and how to proceed with the study. Only after approval of the competent authorities and ECs/IRBs may the study continue.

In addition, the DMC could make a recommendation for study termination due to concerns over patient safety or issues relating to data monitoring or quality control.

6.13 Removal of Patients from the Trial or Treatment

The investigator may withdraw a patient from the study for any of the following reasons:

- The investigator believes it is in the best interest of the patient to discontinue the study
- The Sponsor or investigator terminates the study
- The patient withdraws consent or requests to be discontinued from the study
- The patient is non-compliant

In case of early withdrawal of the patient, he will be asked to perform the 48 (\pm 4) hour visit assessment after last administration of LR769, unless he has withdrawn Informed Consent.

The investigator may discontinue a patient from LR769 treatment for any of the following reasons:

- AE or SAE possibly related to LR769 treatment
- A clinically significant change in the patient's condition that does not allow safe administration of LR769
- Per judgment of the investigator, if an adequate hemostatic response is not achieved with LR769, and the bleeding requires continued treatment, the treating physician should stop treatment with LR769 and treat the patient with a rescue therapy, such as another bypassing agent (e.g., FEIBA® or NovoSeven®) and/or other effective hemostatic treatment. The patient remains eligible for treatment with LR769 for a new surgical procedure taking into account the pharmacodynamic half-life of the rescue therapy given.

6.14 Replacement of Patients

Patients who are removed from the study will only be replaced if their removal results in the minimum number of surgical or other invasive procedures/patients needed for the study not being met.

6.15 Other Study Procedures

There are no other study procedures.

6.16 Appropriateness of Measurements

Efficacy assessments are performed according to existing guidelines and published literature ([Shapiro and Cooper, 2012](#); [Shapiro, 2014](#); [Shapiro et al., 1998](#); [Giangrande et al., 2009](#)). In this study, response to treatment with LR769 will be assessed intraoperatively by the surgeon/practitioner and postoperatively by the investigator or designee.

7 STUDY ACTIVITIES

All study activities can be found in the Schedule of Events (see [Appendix 1](#)).

7.1 Screening (Days -21 to -1)

- Informed consent signature
- Determine eligibility
- Demographics
- Medical history
- Physical examination
- Clinical safety laboratory tests (hematology, coagulation, serology, chemistry, urinalysis), by local laboratory - per weight requirement
- FVIII/FIX and inhibitor testing, by central laboratory (as confirmed at screening by the institutional lab, with the exception being for patients <12 kg where samples will only be collected for testing at the central laboratory)
- Vital signs
- 12-lead ECG
- Assessment of concomitant medication
- Assessment of AEs

7.2 Surgery/Invasive Procedure and LR769 Treatment

7.2.1 Before Surgery/Invasive Procedure

- Confirm eligibility
- Physical examination (excluding height, including weight, which is the weight to be used for calculating dose of LR769) within 24 hours before the procedure
- An IV bolus dose of 75 µg/kg (for a minor surgery or other minor invasive procedure) or 200 µg/kg (for a major surgery or other major invasive procedure) of LR769 administered within ≤2 minutes before the surgical incision or start of the invasive procedure.
- Predicted surgery/invasive procedure characteristics
- Vital signs (blood pressure, heart rate, respiratory rate, and body temperature [sublingual or tympanic])
- Assessment of concomitant medications
- Assessment of AEs
- Immunogenicity sample (including storage serum sample for future use)

7.2.2 During Surgery/Invasive Procedure

After the initial IV bolus dose of LR769 during the surgical or other invasive procedure, patients will be given repeated IV bolus doses of 75 µg/kg of LR769 administered over ≤2 minutes at least 2 hours apart.

7.2.3 Surgeon/Practitioner's Assessment

Immediately after completion of the procedure, the surgeon will:

- Determine the actual surgery/invasive procedure characteristics (major or minor, duration of procedure, factors that may have influenced bleeding independent of hemostasis, actual type of anesthesia, and complications)
- Estimate the blood loss
- Assess the intraoperative efficacy of LR769

The patient's intraoperative response to treatment with LR769 will be assessed by the surgeon/practitioner and recorded as "excellent," "good," "moderate," or "poor." Further details regarding the criteria for the surgeon/practitioner's assessment of intraoperative efficacy are provided in [Section 6.8](#). The surgeon/practitioner will also record any AEs and concomitant medications.

7.3 After Surgery/Invasive Procedure

The patient will be followed postoperatively according to the site's standard of care. Treatment with LR769 following completion of the surgery or invasive procedure will be administered according to the specifications in [Section 5.2.2](#) (major surgical procedures) or [Section 5.2.3](#) (minor surgical or other invasive procedures).

7.3.1 24 Hours ± 2 Hours After Completion of Procedure

- Clinical safety laboratory tests (hematology, chemistry, urinalysis), by local laboratory; per weight requirement
- Administration of 75 µg/kg of LR769 according to the administration schedule determined by the investigator
- Postoperative assessment
- Vital signs
- Efficacy assessment by investigator or designee if treatment with LR769 is ongoing; assessment may be made by phone if the patient has been discharged home
- Assessment of concomitant medications
- Assessment of AEs (including thromboembolic assessments)

7.3.2 Every 24 Hours \pm 2 Hours After Completion of Procedure

- Efficacy assessment by investigator or designee as long as treatment with LR769 is ongoing); assessment may be made by phone if the patient has been discharged home
- Postoperative assessment
- Assessment of concomitant medications
- Assessment of AEs (including thromboembolic assessments)

7.3.3 7-14 Days After Start of Treatment with LR769

A sample for immunogenicity will be taken 7-14 days after start of treatment. Depending on the timing (length of time since the patient's first dose of LR769), this visit may be combined with another specified visit.

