The investigator or designee will make postoperative efficacy assessments at 24 (± 2) hours after procedure completion, at 24 (± 2) hour intervals while treatment with LR769 is ongoing, after the last dose of LR769, and during follow-up visits. The final assessment (which represents the primary efficacy outcome) will be performed by the investigator at the study center 48 (± 4) hours after the last dose of LR769 and will be based upon the totality of the assessments performed on the patient at each timepoint also taking into consideration the surgeon/practitioner's intraoperative hemostatic assessment, the number of (interventions for) bleeding episodes, oozing, blood transfusions, and the amount of LR769 used. All assessments will be recorded in the patient's record.

Postoperative response to treatment will be rated as follows:

- Excellent: postoperative blood loss similar to or less than expected following this type of procedure in a patient who does not have a bleeding disorder and who is undergoing the same surgical or other invasive procedure; no blood component transfusion is required
- Good: postoperative blood loss greater than expected following this type of procedure in a patient who does not have a bleeding disorder and who is undergoing the same surgical or other invasive procedure, not explained by a surgical/medical issue other than hemophilia; no unexpected need for blood component transfusion
- Moderate: postoperative blood loss that is substantially greater than expected following this type of procedure in a patient who does not have a bleeding disorder and who is undergoing the same surgical or other invasive procedure, not explained by a surgical/medical issue other than hemophilia; additional blood component [within 2-fold greater than expected] transfusion is necessary
- Poor: uncontrolled postoperative blood loss, not explained by a surgical/medical issue other than hemophilia that requires intervention (rescue therapy requirement [bypass agent or porcine FVIII], and/or increased blood component [>2 -fold greater than expected] transfusion, and/or leads to hypotension or unexpected transfer to Intensive

Care Unit [ICU])

Safety Assessments

Safety of treatment with LR769 will be assessed by the following:

- Physical examinations at screening, pre-procedure and 48 (± 4) hours after last dose of LR769

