- Moderate: postoperative blood loss that is substantially greater than expected following this type of procedure in a patient who does not have a bleeding disorder and who is undergoing the same surgical or other invasive procedure, not explained by a surgical/medical issue other than hemophilia; additional blood component [within 2-fold greater than expected] transfusion is necessary
- Poor: uncontrolled postoperative blood loss, not explained by a surgical/medical issue other than hemophilia that requires intervention (rescue therapy requirement [bypass agent or porcine FVIII], and/or increased blood component [>2 -fold greater than expected] transfusion, and/or leads to hypotension or unexpected transfer to Intensive Care Unit [ICU])

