7.2 Definition of Baseline, Study Visits, and Visit Windows

Baseline is defined as the last available assessment prior to first study drug dose.

For Post-Operative assessments timepoints will be assigned according to Protocol-specified visit windows. Assessment occurring 24 (\pm 2) hours from procedure completion will be assigned to the 24-hour timepoint, and so on every 24 hours, creating timepoints for 48, 72... hours.

All other analyses will use the visits and time points as reported in the eCRF. No further reassignment of the visits will be done.

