7.7.1 Analysis of Primary Efficacy Endpoint

The primary efficacy endpoint is the percentage of surgical or other invasive procedures with a “good” or “excellent” response to LR769 treatment, as assessed by the investigator at the study center 48 (\pm 4) hours after the last administration of LR769; this assessment will be based upon the totality of assessments performed on the patient at each timepoint, also taking into consideration the surgeon’s intraoperative hemostatic assessment, the number of (interventions for) bleeding episodes, oozing, blood transfusions, and the amount of LR769 used. An additional sensitivity analysis will be performed in which patients whose 48-hour assessment is missing are treated as failures.

The proportion of “good” and “excellent” responses at 48 (\pm 4) hours will be summarized. Clopper-Pearson exact 95% confidence interval for proportion will be calculated for each surgery type and age group and overall. The summaries will include missing assessments in percent calculation, while they will still be discarded when calculating the proportion of successes and the confidence interval (CI). The missing values imputed as per section 7.3 of this SAP will be analyzed as imputed.

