7.7.2 Analysis of Secondary Efficacy Endpoints

The following endpoints are considered secondary for this study:

- Percentages of success as defined as the combination of “good” and “excellent” responses by the investigator or designee for all efficacy timepoints other than the primary
- Percentages of “poor,” “moderate,” “good,” and “excellent” response by the investigator or designee for all efficacy timepoints
- Percentages of success as defined as the combination of “good” and “excellent” responses by the surgeon/practitioner for the intraoperative period
- Percentages of “poor,” “moderate,” “good,” and “excellent” response by the surgeon/practitioner for the intraoperative period
- Intraoperative blood loss determined by the surgeon/practitioner as compared to the surgeon/practitioner’s maximum predicted blood loss
- Number of events requiring transfusion between start of procedure and 48 (±4) hours after last administration of LR769
- Changes in hemoglobin between start of procedure and 48 (±4) hours after last administration of LR769
- Amount of LR769 used. Total, and separated by use in hospital, at home, or for specific reasons (eg, physical therapy, or other reasons like drain or suture removal)
- Number and type of bleeding episodes at the surgical site between start of procedure and 48 (±4) hours after last administration of LR769
- Number of surgical interventions/re-explorations for bleeding episodes between start of procedure and 48 (±4) hours after last administration of LR769

The first four secondary endpoints will be analyzed similarly to the primary endpoint: numbers and percentages of successes will be summarized at each timepoint, together with their Clopper-Pearson exact confidence limits.

Difference between the expected and actual blood loss will be calculated for each surgery in the study and then summarized together with 95% confidence limits. Number of events requiring transfusion, Number of bleeding episodes (by type) at the surgical site between start of procedure and 48 (±4) hours, and Number of surgical interventions/re-explorations for bleeding episodes between start of procedure and 48 (±4) hours after last administration of LR769 will be analyzed similarly.

Hemoglobin levels will be summarized at baseline and at 48 (±4) hours after last administration of LR769. Changes from baseline will also be summarized for 48 (±4) hours timepoint. 95% confidence limits for the changes will be displayed.

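### Daily secondary success percentages are in effect restricted to procedures still on LR769, so a rescued procedure is absent, not a failure, at later timepoints

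*Protocol*

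**What the plan says.** **When ratings are made.** Protocol 7.3.1 asks at 24 hours for "Efficacy assessment by investigator or designee if treatment with LR769 is ongoing". Protocol 7.3.2 repeats the condition for each later 24-hour point: "Efficacy assessment by investigator or designee as long as treatment with LR769 is ongoing". The synopsis section on postoperative assessment says the same and adds the off-treatment ratings: "hour intervals while treatment with LR769 is ongoing, after the last dose of LR769, and during follow-up visits". Protocol 7.4, 7.5 and 7.6.1 schedule ratings at last dose, at early termination and 48 hours after last dose.

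**What ends LR769.** Under Protocol 6.13, if the response is inadequate and bleeding needs continued treatment, "the treating physician should stop treatment with LR769 and treat the patient with a rescue therapy". LR769 also ends when hemostasis has been achieved. Minor procedures have a 2-day minimum, with shorter treatment allowed for some; major procedures have a 5-day minimum (Protocol 5.2.2 and 5.2.3).

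**How ratings are analysed.** SAP 7.2 assigns daily ratings by time from procedure completion, "creating timepoints for 48, 72... hours". SAP 7.7.2 treats the first four secondary endpoints like the primary: "numbers and percentages of successes will be summarized at each timepoint". SAP 7.7.1 shows missing ratings in the category percentages, "while they will still be discarded when calculating the proportion of successes" and the confidence interval. By default, SAP 7.1 uses non-missing observations as the denominator.

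**What is imputed.** The SAP 7.3 imputation to Poor covers only the final assessment and needs two joint conditions. The missing-as-failure sensitivity analysis in SAP 7.7.1 belongs to the primary endpoint. SAP 7.3 rules out any other imputation.

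**The concern.** Whether a daily rating exists depends on the outcome being rated. Inadequate hemostasis leads to rescue, rescue ends LR769, and the end of LR769 ends the interval ratings. No SAP rule then carries the failure forward, so the procedure is simply absent from the 48-hour, 72-hour and later success percentages.

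At stake is the secondary endpoint of success at every timepoint other than the primary. Read down the column, it can appear to show hemostasis improving over time when part of the change is a change in who is still rated. The planned minimum is 12 procedures, and the tables are also split by surgery type and age group, so one or two lost failures are visible in the percentages.

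**Working it through.** The plan gives no expected rate or power figure to reproduce. The check compares denominators.

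**Inputs from the documents**
- N = 12, the minimum number of procedures (Protocol 3.3, SAP 4), at least 6 of them major.
- Two-sided 95% Clopper-Pearson intervals (SAP 7.7.1).

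**Assumed inputs, at a given daily timepoint**
- c = procedures that stopped LR769 after success (0 or 6). Six is plausible after about 48 hours if the minor procedures have finished and the 6 major ones continue.
- r = procedures stopped and rescued (1 or 2).
- b = procedures still on LR769 but rated moderate or poor (0 to 2).
- s = N − c − r − b = successes still on LR769.

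**Formulas**
- Planned, in effect: s / (N − c − r).
- Fixed denominator, rescue as non-success, completers keeping success: (s + c) / N.

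**Step 1: removing rescues alone.** Compare s/(N − c − r) with s/(N − c). The first is larger whenever r > 0 and s > 0. With c = 6, r = 1, b = 0, it is 5/5 = 100% against 5/6 = 83.3%. This part of the effect has one direction only.

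**Step 2: against all procedures.** The non-success fractions are b/(N − c − r) as planned and (b + r)/N on the fixed denominator. The planned figure is too high only if b × N < (b + r)(N − c − r).

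| c | r | b | As planned | All 12 procedures | Planned figure is |
|---|---|---|---|---|---|
| 0 | 1 | 0 | 11/11 = 100% (71.5-100) | 11/12 = 91.7% (61.5-99.8) | higher |
| 0 | 2 | 0 | 10/10 = 100% (69.2-100) | 10/12 = 83.3% (51.6-97.9) | higher |
| 6 | 1 | 0 | 5/5 = 100% (47.8-100) | 11/12 = 91.7% (61.5-99.8) | higher |
| 6 | 2 | 1 | 3/4 = 75.0% (19.4-99.4) | 9/12 = 75.0% (42.8-94.5) | equal |
| 6 | 1 | 1 | 4/5 = 80.0% (28.4-99.5) | 10/12 = 83.3% (51.6-97.9) | lower |
| 6 | 1 | 2 | 3/5 = 60.0% (14.7-94.7) | 9/12 = 75.0% (42.8-94.5) | lower |

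Checking the rule on the fifth row: b × N = 12 and (b + r)(N − c − r) = 2 × 5 = 10. Since 12 > 10, the planned figure is too low. On the fourth row both sides equal 12.

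**Step 3: a tempting repair.** Adding only the rescued procedures back to those on LR769 does not work, because completers still leave. With one rescue and 11 successes, that percentage runs 5/6 = 83.3% once six have completed, 1/2 = 50% when one success remains on LR769, and 0/1 = 0% after that. Over all procedures it is 11/12 = 91.7% throughout.

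**The case against.** Several points on the other side stand.

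- **Ratings do not all stop with LR769.** Rescued procedures are still due ratings at last dose and 48 hours after it, or at early termination. Their failure can be recorded there. What is missing is any rule that takes it to the later daily timepoints.
- **The denominator is inferred.** No sentence states it; it follows from the protocol schedule combined with the SAP missing-data rule. The synopsis design section and SAP 3.1 describe 24-hourly ratings without the on-treatment condition. The SAP does not say whether a rating that was not due counts as missing. If it does, it appears in the category percentages but still not in the success proportion.
- **Rescue is not automatically Poor.** The scale lists blood loss "that requires intervention (rescue therapy requirement [bypass agent or porcine FVIII" and other interventions, but the loss must also be uncontrolled and not attributable to a surgical or medical cause other than hemophilia. A reader might infer that any use of rescue settles the rating; the definition does not support that.
- **An on-treatment summary is legitimate** as a description of response to LR769, provided it is labelled as one. These are descriptive secondary endpoints, and individual ratings will be listed.

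These points limit the size of the problem. They do not supply the missing rule.

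**Conclusion.** The concern holds for the daily secondary timepoints. Under the plan as written, a procedure stopped for inadequate hemostasis and rescued drops out of every later daily success percentage, and that alone pushes the percentage up.

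Two stronger conclusions might be drawn and are not supported. The first is that later timepoints overstate success overall. Completers leave too, so against all procedures the figure can be too high, equal or too low. What can be said is that the percentages at different timepoints describe different, selected sets of procedures. The second is that the primary endpoint is inflated in the same way. It is timed from the last LR769 dose, and a rescued procedure is still due that rating; missing primary ratings are a separate question.

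In the illustrations without other non-successes, one rescue in 12 moves the figure from 91.7% to 100%, and two rescues move it from 83.3% to 100%. The rescue, completion and non-success counts are assumptions, since the documents give none. The change is worth making before database lock because it is cheap, but no test or decision rule depends on these percentages.

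**What to change.** In SAP 7.7.2, for each daily timepoint:

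1. Use a fixed denominator of all procedures in the Efficacy Population.
2. Count a procedure as non-success from the time LR769 was stopped for inadequate hemostatic response, or rescue was given for that reason. For this flag, rescue means the bypassing agents or porcine FVIII named in the Poor definition, not the antifibrinolytics that Protocol 5.6.1 permits.
3. Let procedures that completed LR769 keep their last observed rating.
4. Show the numbers on LR769, completed, rescued and otherwise unrated at each timepoint. On a fixed denominator, an otherwise unrated procedure falls among the non-successes unless the SAP says differently, so state that rule too.
5. If an on-treatment percentage is kept, label it as such.

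This changes analysis only. It costs SAP wording and one derived flag; Protocol 5.5 already records concomitant therapy with date, time and dose, and Protocol 6.8 records the ratings. The downside is somewhat less favourable secondary percentages where rescues occur.
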